8.4. Insurance

The Sponsor has covered this clinical study by means of an insurance of the clinical study according to national requirements. The name and address of the relevant insurance company,

the certificate of insurance, the policy number and the sum insured are provided in the Investigator's Site File.

8.5. Informed Consent

The subjects shall be informed of the nature, significance, implications and risks of the trial, and informed consent will be freely given and evidenced in writing, dated and signed, or otherwise marked, by the subject as evidence to indicate his/her free informed consent, prior to the start of the study.

The nature of the informed consent will comply with the Declaration of Helsinki, the current requirements of GCP (EMA/CHMP/135/1995) and local regulation which ever offers the greater subject protection.

8.6. Changes to the Protocol and Informed Consent Form

Study procedures will not be changed without the mutual agreement of the PI and AstraZeneca.

If there are any substantial changes to the study protocol, then these changes will be documented in a study protocol amendment and where required in a new version of the study protocol.

If a protocol amendment requires a change to the ICF the IEC should approve the revised ICF before the revised form is used.

If local regulations require, any administrative change will be communicated to or approved by the IEC.

9. DATA QUALITY ASSURANCE AND DATA MANAGEMENT

9.1. Quality Control and Source Data Verification

Source data verification will be conducted with due regard to subject confidentiality.

The Clinical Unit will allow the study monitor and Sponsor representative direct access to all study documents, medical files and source documents to enable verification of the study data, while maintaining the anonymity of the subject and confidentiality of the data.

Internal quality control will be performed at all stages of the study by the Clinical Unit.

9.2. Audit/Inspections

The Clinical Unit facilities and all study data/documentation may be audited/inspected by independent auditor/inspector/any representatives of regulatory authorities. The PI must allow the applicable persons access to all relevant facilities and data/documents. The PI must be available to discuss any findings/issues.

If an audit was performed, the audit certificate will be included in the CSR.

9.3. Study Monitoring

The conduct of the study will be monitored by an independent Parexel monitor to ensure compliance with applicable regulatory requirements and GCP. The summary of the documentation of the monitoring visits will form part of the study documentation and will be archived as such.

Monitoring visits at site will be limited to a minimum, required as deemed appropriate during COVID-19 pandemic.

9.4. Data Collection

The ClinBase™ system is an electronic source data capturing and information management system. The system combines all aspects of source data capturing with process control and clinical study management. All clinical and laboratory data, except those which are paper-based or provided by an external vendor, will be collected in ClinBase™. Only paper-based data will be subject to data entry. For electronic source data, no data entry will be performed.

The responsible study monitor will check data at the monitoring visits to the Clinical Unit. The PI will ensure that the data collected are accurate, complete and legible. Data will be monitored within ClinBase™ by the study monitor before being exported. Any changes made during monitoring will be documented with a full audit trail within ClinBase™.

9.4.1. Case Report Forms and Source Documents

All data obtained using paper collection methods during the clinical study will be recorded in ClinBase™. All source documents from which ClinBase™ entries are derived should be placed in the subject's personal records.

The original ClinBase™ entries for each subject will be checked against source documents by the study monitor. Instances of missing or uninterpretable data will be discussed with the PI for resolution.

9.4.2. Access to Source Documents

During the course of the clinical study, a study monitor will make Clinical Unit visits to review protocol compliance, compare ClinBase™ entries and individual subject's personal records, assess IMP accountability and ensure that the clinical study is being conducted according to pertinent regulatory requirements. ClinBase™ entries will be verified against source documents. The review of medical records will be handled confidentially to ensure subject anonymity.

Checking of the ClinBase™ entries for completeness and clarity and verifying with source documents, will be required to monitor the clinical study for compliance with GCP and other regulations. Moreover, regulatory authorities of certain countries, IECs may wish to carry out source data inspections on-site, and the Sponsor's clinical quality assurance group may wish to carry out audits. Direct access to source data will be required for these inspections and audits; they will be carried out giving due consideration to data protection and subject confidentiality. The PI assures the Sponsor of the necessary support at all times.

9.5. Data Management

Parexel will utilise standardised and validated procedures and systems to collect, process and file the clinical data of this study. Any system used will be compliant with FDA 21 CFR Part 11 requirements.

A DMP will be prepared to describe the processes and data-flow within the clinical study. Timelines, versions for the computer systems and the coding will be defined in the DMP, and if applicable, sponsor specific requests will also be documented within. The DMP will be finalised before first dose where possible but before database lock.

A DVS will be created to outline the validation checks to be performed during the study. The DVS must be finalised before data validation.

After the data has been monitored by the responsible study monitor all data received will be reviewed, logged and filed.

The raw data intended for further processing will be checked by standard routines or according to the DVS and queries will be generated and sent to the PI for review and resolution. Corrections resulting from these queries will be confirmed on the DCFs. This process will be repeated until no further discrepancies are found. The data will then be declared as clean. Applicable documentation will be stored in the study files.

Only trained study staff will have access to the clinical database and every change in data will have a full audit trail.

10. EVALUATION AND CALCULATION OF VARIABLES

10.1.1. Adverse Events

All AEs will be coded using MedDRA vocabulary and will be listed for each subject.

Adverse events will be assigned to a treatment based on the start date/time of the AE in relation to dosing in that period; for tabulation purposes the AE will then be assigned to the treatment received in the respective treatment period as follows:

- Treatment Period 1: AEs with start date/time at the time of or after dosing in Treatment Period 1 until the time of dosing in Treatment Period 2.
- Treatment Period 2: AEs with start date/time at the time of or after dosing in Treatment Period 2 until the time of dosing in Treatment Period 3.
- Treatment Period 3: AEs with start date/time at the time of or after dosing in Treatment Period 3 until the time of dosing in Treatment Period 4.
- Treatment Period 4: AEs with start date/time at the time of or after dosing in Treatment Period 4 until the time of dosing in Treatment Period 5.
- Treatment Period 5: AEs with start date/time at the time of or after dosing in Treatment Period 5 until the final Follow up Visit.

Adverse events with missing start dates/times will be handled as follows:

- If the start date is completely missing but the end date is known and shows that the AE ended on or after the first dose date, then the start date will be imputed as the first day of dosing; if the end date is known and shows that the AE ended before the first dose date, then the screening date will be used for the start date. If the end date is non-informative (ie, is missing or does not contain enough information), the start date will be imputed as the first date of dosing.
- If only the start day is missing the day will be imputed as the first day on which a dose was given in that month unless the end date is known and shows that the AE ended before a dose was given in that month; in which case the date will be imputed as 01. If the end date is non-informative (ie, is missing or does not contain enough information), the start date will be imputed as the first date of dosing in the known month. If the month is not a dosing month the date will be imputed as 01.
- If the start day and month are missing the date will be imputed as the first day of dosing in the known year unless the end date is known and shows that the AE ended before a dose was given in that year; in which case the start day and month will be imputed as 01Jan or with the date of screening if this is later. If the end date is non-informative (ie, is missing or does not contain enough information), the start date will be imputed as the first date of dosing in the known year. If the year is not a year of dosing then the date will be imputed as 01Jan or with the date of screening if this is later.
- Missing times will be imputed as 00:00 h or with the time of dosing for events starting on a dosing day.

For purposes of the AE summaries, the following will apply:

- AEs with unknown intensity will be treated as “severe” for the tabulations.
- AEs with unknown relationship will be treated as “related” for the tabulations.
- AEs with unknown seriousness will be treated as “serious” for the tabulations

There will be no imputation of AE data for the data listings. All data will be listed as recorded in the CRF.

Adverse events with onset (start date/time) after dosing in Treatment Period 1 will be summarised by treatment (where treatments will be pooled across treatment periods) and overall for all subjects, including tabulations by causality and severity (mild, moderate and severe). All tabulations will be presented by SOC and Preferred Term with the exception of the causality and severity tables, which will be presented by Preferred Term only. Furthermore, separate listings of SAEs, DAEs and AEs that led to death will be presented.

Adverse events will be listed and the following information will be included in the listings: verbatim term, SOC, PT and lowest level term, start date/time, end date/time, time from last dose, causality, action taken, whether the AE was classified as serious and the outcome.

All tabulations will include the number and percentage of subjects. In addition, a separate tabulation will be presented showing the number of events by treatment and PT.

Finally, an overview of all AEs will be presented, separately for the number and percentage of subjects and the number of events. This will include categories for any AE, AEs with outcome of death and SAEs.

10.1.2. Laboratory Assessments

Haematology and clinical chemistry values will be listed by subject and time point including changes from baseline and repeat/unscheduled measurements. Summary tabulations including absolute values and changes from baseline will be presented by time point for the safety analysis set. The baseline for the measurements in Treatment Period 1 will be the Day -2 assessment and for the measurements in Treatment Period 2, 3, 4, and 5, it will be the Day -1 assessment performed prior to dosing in each of the respective treatment periods. Shift tables will also be presented.

Any laboratory variables with results from the laboratory given as “< xx” or “>xx” in the database will be imputed with the absolute value of the number without the sign (eg, < 2.2 will be imputed as 2.2) for the descriptive statistics and changes from baseline.

The listings will include the following information: test name, date of measurement, reference range, result and flags for any measurements that are outside the reference range (eg, AstraZeneca, program, or laboratory ranges). Clinical laboratory data will be reported in System International units in the CSR.

Additional listings will be presented for the following:

- Urinalysis (macroscopic and microscopic, if applicable)
- Pregnancy testing (including FSH)
- The results of viral serology, SARS-CoV-2 virology, and the drugs of abuse, alcohol, and cotinine screen will not be listed in the CSR.

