Treatment 1: verinurad prolonged release HPMC capsule 12mg and allopurinol tablet 300mg, as a free combination, fasted state.

Treatment 2: verinurad/allopurinol FDC capsule 12/300 mg, fasted state.

Treatment 3: verinurad/allopurinol FDC capsule 12/300 mg, fed state.

Treatment 4: verinurad prolonged release HPMC capsule 12mg and allopurinol tablet 300mg, as a free combination, fed state.

Treatment 5: verinurad prolonged release gelatin capsule 12 mg, fasted state.

IMP: Investigational Medicinal Product.

Table 3-1 Schedule of Assessments

	Screening	Admission	Treatment Periods 1, 2, 3, 4, and 5		Follow-up Visit	Corresponding Section in Protocol
Visit	1	2		3		
Study Day	Day -28 to -3	Day -2	Day -1	Day 1 to 4	7 to 14 days post final dose	
Inclusion/exclusion criteria	X	X	X ^a			Sections 4.1.1 and 4.1.2
Demographic data	X					Section 11.2.3.1
Medical history	X					Section 11.2.3.1
Urinary drug/alcohol/cotinine screen	X	X				Section 6.3.2.8
Serology	X					Section 6.3.2.6
Informed consent	X					Section 8.5
HLA-B*58:01 allele genotyping	X					Section 6.3.2.3
Randomisation			X ^b			Section 5.1.1
Study Residency:						
Check-in		X (in the morning) ^c				Section 3.1
Check-out				Day 4 (after 72 h post-dose assessments) ^c		Section 3.1
Non-residential visit	X				X	Section 3.1
Verinurad and Allopurinol (verinurad only for Treatment 5) Administration:				Day 1 (0 h)		Sections 3.1 and 5.4.3

	Screening	Admission	Treatment Periods 1, 2, 3, 4, and 5		Follow-up Visit	Corresponding Section in Protocol
Visit	1	2		3		
Study Day	Day -28 to -3	Day -2	Day -1	Day 1 to 4	7 to 14 days post final dose	
Safety and Tolerability:						
Tympanic temperature ^d	X	X	X ^e	X	X	Section 6.3.5
Adverse event questioning and reporting ^f	X	X	X ^e	Spontaneous plus Day 1: pre-dose, 3 and 12 h post-dose Day 2: 24 h post-dose Day 3: 48 h post-dose Day 4: 72 h post-dose	X	Section 6.3.1
Prior and concomitant medications questioning	X	X	X ^e	X	X	Section 11.2.4.1
Blood pressure and pulse (supine)	X	X	X ^e	Day 1: Pre-dose Day 4: 72 h post-dose	X	Section 6.3.5
Safety 12-lead electrocardiograms	X				X	Section 6.3.4
Clinical laboratory evaluations ^g	X	X	X ^e		X	Section 6.3.2
Physical examination	X	X (brief)	X (brief) ^e	Day 4: 72 h post-dose (brief)	X	Section 6.3.3
Body weight and height, BMI	X					
Pregnancy test ^h	X	X			X	Section 6.3.2.5
COVID-19 Assessments						
Pre-visit phone call ⁱ	X	X			X	
SARS-CoV-2 RT-PCR		X ^j				Section 6.3.2.7
SARS-CoV-2 antibody	X					Section 6.3.2.7

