	Screening	Admission	Treatment Periods 1, 2, 3, 4, and 5		Follow-up Visit	Corresponding Section in Protocol
Visit	1	2		3		
Study Day	Day -28 to -3	Day -2	Day -1	Day 1 to 4	7 to 14 days post final dose	
Pharmacokinetics						Section 6.4.1
Pharmacokinetic sampling for verinurad, allopurinol and oxypurinol ^k				Day 1: Pre-dose, 0.5, 1, 1.5, 2, 3, 4, 5, 6, 8, 10 and 12 h post-dose Day 2: 24 and 36 h post-dose Day 3: 48 h post-dose Day 4: 72 h post-dose		
Pharmacodynamics						Section 6.5.1
Pharmacodynamic sampling for sUA			-24, -23, -22, -21, -20, -19, -18, -16, -14 and -12 h ^l	Day 1: Pre-dose, 1, 2, 3, 4, 5, 6, 8, 10 and 12 h post-dose Day 2: 24 h, Day 3: 48 h post-dose, Day 4: 72 h post-dose h post-dose		

- ^a Eligibility criteria will be reconfirmed on Day -1 of Treatment Period 1, prior to randomisation.
- ^b Randomisation will take place on Day -1 of Treatment Period 1, after eligibility has been reconfirmed.
- ^c Subjects will be admitted to the Clinical Unit on Day -2 and will remain residential until they are discharged on Day 4 of Treatment Period 5.
- ^d Tympanic temperature will be measured at least once daily (in the morning) on the days of assessment.
- ^e Applicable to Day -1 of Treatment Periods 2 to 5 only.
- ^f Adverse events will be collected from the start of randomisation throughout the treatment periods up to and including the Follow-up Visit. Serious adverse events will be recorded from the time of informed consent.
- ^g Blood (clinical chemistry and haematology) and urine (urinalysis) sample collection. Samples will be collected following an overnight fast.
- ^h Serum pregnancy tests will be performed at Screening. Urine pregnancy test will be performed at admission (Day -2 of Treatment Period 1) and the Follow-up Visit.

- ⁱ Phone calls will be made 1 day prior to each visit to record signs and symptoms of COVID-19 or any contact with persons having confirmed SARS-CoV-2 infection. In case of signs or symptoms or contact, the visit will be cancelled and the reason for cancellation will be appropriately documented.
- ^j At the discretion of the investigator, an unscheduled SARS-CoV-2 RT-PCR can be performed in case of any signs or symptoms of COVID-19.
- ^k Samples for allopurinol and oxypurinol will not be collected for Treatment 5.
- ^l Applicable to Treatment Period 1 only.

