3.3. Risk-benefit Assessment

There are no direct benefits for the subjects participating in this study. However, study-related health assessments are provided without costs for the subjects. The major risks for subjects who participate in the study will come from IMP administration. In addition, there might be a slight risk of infection or bruising that might occur after insertion of an intravenous cannula for frequent blood sampling. Subjects may experience slight skin irritation from the adhesive on the ECG electrodes. These procedural effects are generally mild and clear up completely within a few days.

The main toxicity concern noted with verinurad monotherapy in healthy subjects is serum creatinine elevations $>1.5 \times$ baseline, which occurred in 1.7% of healthy subjects. A change from baseline of ≥ 0.3 mg/dL was reported for 6.8% of all subjects. There was no apparent relationship between serum creatinine elevations and dose of verinurad. The creatinine elevations were primarily transient, and often resolved despite continued dosing with verinurad. In order to mitigate the risk in this study verinurad is administered with an XOI, except for Treatment 5, and appropriate hydration is mandated. Further information is provided in the IB [1].

In previous studies, verinurad combined with allopurinol was well tolerated and associated with acceptable side effects. Most AEs were minor and not related to treatment.

Allopurinol is an approved XOI. Most common AEs noted in the prescribing information are rash and blood thyroid-stimulating hormone increased. Allopurinol hypersensitivity reactions can manifest in many different ways, including maculopapular exanthema, hypersensitivity syndrome (also known as DRESS) and SJS/TEN. The HLA-B*58:01 allele has been shown to be associated with increased risk of developing allopurinol-related hypersensitivity syndrome and SJS/TEN. The frequency of the HLA-B*58:01 allele varies widely between ethnic populations: up to 20% in the Han Chinese population, 8 to 15% in the Thai population, about 12% in the Korean population and 1 to 2% in individuals of Japanese or European origin. At the Screening Visit, the subject's HLA-B*58:01 status will be tested and carriers of HLA-B*58:01 will be excluded [1].

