7.1. Total Blood Volume

The approximate total amount of blood to be collected from each subject in this study, excluding repeat samples, is summarised in Table 7-1.

Table 7-1 Total Blood Volume

	Volume per Sample	Number of Samples	Total
Clinical Laboratory:			
Haematology	2.7 mL	7	18.9 mL
Clinical chemistry ^a	7.5 mL	7	52.5 mL
HLA-B*58:01 allele genotyping	3.0 mL	1	3.0 mL
SARS-CoV-2 antibody ELISA	2.6 mL	1	2.6 mL
Pharmacokinetics:			
Verinurad sampling	2 mL	80	160 mL
Allopurinol, and oxypurinol sampling	2 mL	64	128 mL
Pharmacodynamics:			
sUA	1.1 mL	75	82.5 mL
Total			447.7 mL

^a When applicable, serology, serum pregnancy (females only) and follicle stimulating hormone analyses will be performed on the sample collected for clinical chemistry analyses.

ELISA: enzyme-linked immunosorbent assay; HLA: human leukocyte antigen; SARS-CoV-2: severe acute respiratory syndrome coronavirus 2; sUA: Serum uric acid.

Repeat blood samples may be collected for safety reasons. The maximum volume to be drawn from each subject must not exceed 500 mL.

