11.2.5. Safety and Tolerability

All safety data (scheduled and unscheduled) will be presented in the data listings. Continuous variables will be summarised using descriptive statistics (n, mean, SD, minimum, median, maximum) by treatment. Categorical variables will be summarised in frequency tables (frequency and proportion) by treatment. The analysis of the safety variables will be based on the safety analysis set.

Adverse events will be summarised by Preferred Term and SOC using MedDRA vocabulary. Furthermore, listings of SAEs and adverse events that led to withdrawal will be made and the number of subjects who had any AE, SAEs, AEs that led to withdrawal, and AEs with severe intensity will be summarised. Adverse events that occurred from time of informed consent until first administration of IMP will be reported separately.

Tabulations and listings of data for vital signs, clinical laboratory tests and ECGs (listings only) will be presented. Any new or aggravated clinically relevant abnormal medical physical examination finding compared to the baseline assessment will be reported as an AE. Data will be summarised for the observed values at each scheduled assessment, together with the corresponding changes (and/or percentage change) from the baseline when baseline is defined. Clinical laboratory data will be reported in the units provided by the clinical laboratory for the SRC meeting, and in Système International units in the CSR.

Out-of-range values for safety laboratory, vital signs and ECG will be flagged in individual listings as well as summarised descriptively using agreed standard reference ranges and/or extended reference ranges (eg, AZ, program, or laboratory ranges).

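### Section 10.1.2 uses each laboratory draw after doses 1 to 4 only as the next period's baseline, so scheduled changes and shifts exist for Period 5 alone (25 of 125 subject-periods)

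*Protocol*

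**What the plan says.** **Schedule.** In Table 3-1 (Section 3.1) the row "Clinical laboratory evaluations" is marked at Screening, Day -2, Day -1 and Follow-up. The Day 1 to 4 cell is empty. Footnote e restricts the Day -1 mark: "Applicable to Day -1 of Treatment Periods 2 to 5 only". Table 7-1 (Section 7.1) lists seven samples each for haematology and clinical chemistry; the haematology row reads "Haematology 2.7 mL 7 18.9 mL".

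**Baseline.** Section 10.1.2 says "The baseline for the measurements in Treatment Period 1 will be the Day -2 assessment", and for Periods 2 to 5 "it will be the Day -1 assessment performed prior to dosing in each of the respective treatment periods".

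**Output.** The same section promises "Summary tabulations including absolute values and changes from baseline will be presented by time point for the safety analysis set", and shift tables as well. Section 11.2.5 summarises safety variables by treatment and adds "Data will be summarised for the observed values at each scheduled assessment, together with the corresponding changes" from baseline, where a baseline is defined.

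**Related text.** Section 10.1.1 assigns an adverse event that starts after one dose and before the next to the treatment given at the earlier dose. Section 3.3 names serum creatinine elevation as the main toxicity concern for verinurad alone, and says "The creatinine elevations were primarily transient, and often resolved despite continued dosing with verinurad". Section 11.2.1 says that no separate SAP will be written, so the rule in 10.1.2 is the operative one.

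**The concern.** A period-specific baseline is useful only if the same period also has a later measurement. Vital signs have one: Section 10.1.5 uses the Day 1 pre-dose value as baseline, and Table 3-1 adds a 72 h value on Day 4. Laboratory tests do not. The first scheduled draw after each of doses 1 to 4 falls on Day -1 of the next period, and 10.1.2 names that draw as the next period's baseline. No text also names it as the post-dose value of the treatment just given.

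At stake are the change-from-baseline and shift tables for haematology and chemistry, including creatinine. As written, they would be empty for most dosed periods. Where they are not empty, they would rest on one sequence per treatment and one late sample. The protocol would also treat the same Day -1 finding in two ways. If it is reported as an adverse event, it belongs to the preceding treatment. As a laboratory value, it is the starting point of the next one.

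**Working it through.** **Step 1. Reproduce the plan's sample count.** From Table 3-1 and footnote e: Screening 1 + Day -2 1 + Day -1 of Periods 2 to 5 4 + Follow-up 1 = 7. Table 7-1 gives 7 for haematology and 7 for clinical chemistry. The match shows that the empty Day 1 to 4 cell is intended and that no post-dose draw is planned within a period.

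**Step 2. Class each draw under the 10.1.2 rule.**

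| Draw | Role under 10.1.2 | Post-baseline value for |
|---|---|---|
| Screening | before the study baseline | none |
| Day -2 | baseline, Period 1 | none |
| Day -1, Period 2 | baseline, Period 2 | none |
| Day -1, Period 3 | baseline, Period 3 | none |
| Day -1, Period 4 | baseline, Period 4 | none |
| Day -1, Period 5 | baseline, Period 5 | none |
| Follow-up | after baseline | Period 5 |

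Scheduled post-baseline values per period are 0, 0, 0, 0 and 1.

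**Step 3. Count subject-periods.** With 25 subjects completing five periods there are 25 × 5 = 125 dosed subject-periods. Those with a scheduled change number 25 × 1 = 25, and 25/125 = 20%. The other 80% have none.

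**Step 4. Split by treatment.** The sequences in Section 11.4 are 12345, 23451, 34512, 45123 and 51234, with 25/5 = 5 subjects each. Each treatment is last in exactly one of them: Treatment 5 in the first, then 1, 2, 3 and 4. Each treatment therefore has a change in 5 of 25 subjects. With 20 completers balanced over sequences, it is 4 of 20 (20 of 100 subject-periods).

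**Step 5. Timing.** The only post-baseline draw is 7 to 14 days after dose 5. At the minimum 5-day spacing of doses, the next period's Day -1 draw comes 5 − 1 = 4 days after the preceding dose, and later if the spacing is longer.

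**Step 6. Effect of pairing each baseline with the next scheduled draw.** Every period then has one baseline and one later value, so 25 × 5 = 125 changes are available instead of 25, with no new sample.

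**The case against.** The strongest defence is that 10.1.2 says which draw is each period's baseline but does not say that a draw may serve only once. The Day -1 draw of Period 2 could also close Period 1, and the adverse event windows in 10.1.1 point that way. The pairing is indeed not forbidden. But it is stated nowhere, and Table 3-1 attaches those draws to Periods 2 to 5. A programmer following the text would produce changes for Period 5 only.

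Several stronger readings should be resisted.

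- A reader might infer that laboratory changes exist for one treatment only. That is true within a subject. Across the trial each treatment has about five values.
- A reader might infer that a rise after any dose would show as a fall under the next treatment. In Periods 2 to 4 no change is computed, so none can appear. Only in Period 5 could a rise persisting from dose 4 sit in the baseline and show as a fall at Follow-up.
- A reader might infer that safety signals are lost. Sections 10.1.2 and 11.2.5 keep absolute values, listings with unscheduled results, and out-of-range flags. Section 6.3.1.4 has clinically significant deterioration reported as an adverse event, and 10.1.1 credits it to the preceding treatment.
- A reader might take laboratory safety by treatment to be a secondary objective. The objective in Section 2.2 has no treatment split. The by-treatment summary comes from 11.2.5, and 11.2.1 qualifies it as applying where applicable.

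It is also fair to say that these summaries are descriptive, that the study calls itself exploratory, and that the primary pharmacokinetic analysis does not depend on them.

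**Conclusion.** The point holds as a defect in a stated analysis rule. Under 10.1.2 and Table 3-1, scheduled laboratory changes and shifts are available for 25 of 125 subject-periods. That is 5 subjects per treatment, all from the sequence in which the treatment came last and all measured 7 to 14 days after dosing. The promised tables are unavailable for 80% of dosed periods, and the rule conflicts with the attribution of adverse events in 10.1.1.

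The counts assume 25 completers, equal sequences and no unscheduled draws. With 20 balanced completers the share is the same and the count per treatment is 4. The 4-day figure assumes the minimum dose spacing.

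The defect does not touch the primary endpoints and does not remove any data from the listings. It merits correction because no separate SAP is planned to repair it, and because the correction needs no new data.

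**What to change.** Amend 10.1.2 so that the next scheduled draw is the post-dose value of the preceding treatment:

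- Period 1: Day -2 to Day -1 of Period 2.
- Periods 2 to 4: own Day -1 to Day -1 of the following period.
- Period 5: own Day -1 to Follow-up.

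Build the shift tables from the same pairs, and attribute each change to the treatment given in between, in line with 10.1.1. Add change from Day -2 as a fixed pre-study baseline. This is needed because, once the pairs are formed, a rise carried into any of the Day -1 baselines of Periods 2 to 5 could appear as a fall.

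State as a limitation that the paired values are taken about 4 days after dosing (7 to 14 days for Period 5), so transient changes may be missed.

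Separately, the sponsor should reconcile the empty Day 1 to 4 laboratory cell with the concern in Section 3.3 about transient creatinine elevations. How that is resolved is a clinical decision, and this point does not prescribe additional monitoring.

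The cost is a few sentences in 10.1.2 and changes to table programming. No extra blood or visit is needed.
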